5.1 Primary Endpoint

The primary efficacy endpoint is the best overall cGVHD response rate during the study based on investigator assessments. To assess the primary endpoint, the study used the 2005 NIH Consensus Panel Response criteria with two modifications based on the updated 2014 NIH Consensus Panel Response criteria: 1) “Not Evaluable” can be used for assessments where there is another non-cGVHD cause for the abnormalities documented and 2) a change in cGVHD organ score from 0 to 1 is no longer considered progression as is the case per the 2005 NIH cGVHD Response Criteria.

Best overall cGVHD response rate is defined as the proportion of subjects who achieve a NIH-defined complete response or partial response. The response rate and its 95% confidence interval (CI) will be calculated based on the exact test for binomial distribution. If the lower bound of the CI of the response rate is $\geq 25\%$, the primary efficacy objective is achieved.

5.2 Secondary Endpoints

In order to preserve the study wise two-sided type I error rate of 0.05, rate of sustained response will be tested at the two-sided significance level of 0.05 if the primary endpoint, best overall cGVHD response rate, achieves statistical significance. Other secondary endpoints will be summarized with descriptive statistics. No formal statistical testing is planned for the other secondary endpoints.

5.2.1 Rate of Sustained Response

Sustained response is defined as NIH-defined response that sustain continuously for at least 5 months (140 days). Considering 3 days visit window allowed by protocol, the bound of sustained response is defined as 137 days. Intermittent SD assessment between response assessments is allowed. Of the total number of subjects who responded to study treatment, the proportion of subjects who meet the sustained response criterion will be summarized in the same manner as the primary endpoint. If the lower bound of the CI of the response rate is $\geq 25\%$, this secondary objective is achieved.

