- Review adverse events and concomitant medications (including corticosteroid requirements)
- Pharmacokinetic sampling for PCYC (pre-dose)
- Pharmacodynamic sampling for PCYC (pre-dose)
- T/B/NK sampling for PCYC (pre-dose before Day 2 drug administration)

During and Post Dose

- Administer ibrutinib at specified dose level
- Pharmacokinetic sampling for PCYC at 1, 2, 4, and 6 hours post-dose
- Pharmacodynamic sampling for PCYC (4 hours after first dose administration)
- T/B/NK sampling for PCYC (4 hours after drug administration)

Week 5, 9, 13, 17, 21, 25 (\pm 3 days)**Predose**

- DLT assessment period ends (Phase 1b Week 5 only)
- Symptom-directed physical examination
- Vital signs and performance status (KPS)
- Photographic imaging of cGVHD (Weeks 5, 13 and 25)
- Hematology
- Serum chemistry
- cGVHD assessment per NIH (Weeks 5, 13 and 25) ([Appendix F](#) and [Appendix G](#))
- Lee cGVHD Symptom Scale (Weeks 5, 13 and 25) ([Appendix E](#))
- Donor/host chimerism testing (Weeks 13 and 25)
- Quantitative serum immunoglobulins (IgA, IgG, and IgM) (Weeks 13 and 25)
- Biomarker sampling (Weeks 5, 12 and 25)
- Pharmacodynamic sampling for PCYC (pre-dose on Weeks 9 and 13)
- T/B/NK sampling for PCYC (pre-dose on Weeks 9 and 13)
- Immunosuppressant level – if applicable
- Review returned subject dosing diary
- Review adverse events and concomitant medications (including corticosteroid requirements)

Post Dose

- Administer ibrutinib at specified dose level, and then dispense remaining amount to subject
- Pharmacodynamic sample collection (4 hours after drug administration on Weeks 9 and 13)
- T/B/NK sampling for PCYC (4 hours after drug administration on Weeks 9 and 13)

Week 37 and every 12 weeks thereafter**Predose**

- Complete physical examination
- Vital signs and performance status (KPS)
- Photographic imaging of cGVHD
- Hematology
- Serum chemistry
- cGVHD assessment per NIH ([Appendix F](#) and [Appendix G](#))
- Lee cGVHD Symptom Scale ([Appendix E](#))
- Donor/host chimerism testing
- Quantitative serum immunoglobulins (IgA, IgG, and IgM)
- Biomarker sampling (Weeks 37 and 49)

- Immunosuppressant level – if applicable
- Review returned subject dosing diary
- Review adverse events and concomitant medications (including corticosteroid requirements)

Post Dose

- Administer ibrutinib at specified dose level, and then dispense remaining amount to subject

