10.2.2. Secondary Efficacy Endpoints

10.2.2.1. Rate of Sustained Response for at Least 5 Months

Sustained response for at least 5 months is defined as NIH-defined complete response or partial response that was sustained for at least 5 months.

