3.3 Missing and Incomplete Data

In order to achieve the goal of a well-conducted clinical study according to Good Clinical Practice, every effort will be made to collect all data. However, despite best efforts, it may be inevitable that some data may be missing or incomplete. In the subject data listing, the available data, including partial data will be presented as they are recorded on the case report forms (CRFs).

Time-to-event or duration-of-event endpoints will be based on the study day rather than visit number or visit label. No imputation of missing values will be performed for efficacy data unless otherwise specified.

No imputation of missing values for safety data will be performed unless otherwise specified.

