3.4 Conventions

Continuous variables will be summarized with descriptive statistics (mean, standard deviation, median, quartiles, minimum, and maximum). Standard deviation can be replaced by standard error for special requirement. Categorical variables will be summarized using frequencies and percentages.

In efficacy analysis, month is calculated by cycle (28 days). For the analysis other than efficacy, the following rules will be used for the days to months/years conversion:

- 1 month = 30.4375 days;
- 1 year = 365.25 days.

All data collected on the CRF will be presented in data listings upon request by the Regulatory agency. All statistical analyses will be performed using SAS® version 9.2 or higher.

4. Subject Information

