8.1 Visit Window for Analysis

Details for target date for each scheduled visit and time interval between scheduled visits are provided in the table below:

Visit	Start Day	Target Day	End Day
Baseline	Last measurement prior to or on the first dose date		
Cycle Visits			
Week 5	2	29	43
Week 13	44	85	127
Week 25	128	169	211
Week 37	212	253	295
Week 49	296	337	379
Week 61	380	421	463
Week 73	464	505	547
Week 85	548	589	631
Week 97	632	673	715
Week x (every 12 weeks, where $x \geq 97$)	$(x-1)*7-40$	$(x-1)*7+1$	$(x-1)*7+43$

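### The 137-day bound for sustained response allows for one moving visit where the interval has two, and SD assessments are permitted inside a response called continuous

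*SAP*

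**What the plan says.** Protocol 10.2.2.1 defines the endpoint as an NIH-defined "complete response or partial response that was sustained for at least 5 months". It gives no day tolerance and does not mention SD.

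SAP 5.2.1 adds three rules:

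- Length: "Sustained response is defined as NIH-defined response that sustain continuously for at least 5 months (140 days").
- Tolerance: "Considering 3 days visit window allowed by protocol, the bound of sustained response is defined as 137 days".
- Gaps: "Intermittent SD assessment between response assessments is allowed". Neither the number nor the length of such SD periods is limited.

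SAP 5.2 makes this the only secondary endpoint with a formal test, carried out if the primary endpoint succeeds. Under SAP 5.2.1 the objective is met if the lower confidence bound, calculated as for the primary endpoint, is at least 25% among responders.

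**The concern.** The tolerance is meant to stop a subject failing merely because a visit took place on an allowed day other than the target. But a duration has two ends, and both can move. A bound reduced by one visit's window can still fail a subject whose visits were both on schedule.

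The SD sentence raises a different issue. Appendix I of the protocol defines overall SD as the absence of CR, PR and PD, and Protocol 7.2.1 judges SD and PD against baseline. An SD assessment after a PR therefore records that the response criteria are not met at that visit, and a full return to baseline is SD rather than PD. Calling the whole span continuous does not fit that, and the protocol's definition does not provide for it.

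The two features pull in opposite directions: the short tolerance can lower the sustained-response rate, and the SD allowance can raise it. At stake is a pass/fail result on a small denominator.

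**Working it through.** **Inputs**

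- Month length (SAP 3.4): "In efficacy analysis, month is calculated by cycle (28 days").
- Response assessments (Protocol 8.2): "cGVHD assessment per NIH (Weeks 5, 13 and 25"), then Week 37 and every 12 weeks.
- Visit window (Protocol 8.2 and Appendix A): 3 days either side at each of these visits.
- Target days (SAP 8.1): Week 5 is Day 29, Week 13 Day 85, Week 25 Day 169, Week 37 Day 253, Week 49 Day 337. The Week 25 row reads "Week 25 128 169 211" (start, target and end day).
- Dating rule (SAP 3.3): "Time-to-event or duration-of-event endpoints will be based on the study day rather than visit number or visit label". The wide analysis windows in SAP 8.1 therefore do not absorb visit shifts.

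**1. The plan's figure.** 5 × 28 = 140 days, and 140 − 3 = 137 days. It reproduces.

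**2. The gap it has to cover.** Week 5 to Week 25 is nominally 169 − 29 = 140 days. With both visits in window the range is 140 − 6 = 134 to 140 + 6 = 146 days. Visits on Day 32 and Day 166 are both on schedule and 134 days apart. Counting both end days gives 135, which still fails 137.

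**3. How often.** Let each visit's offset be any whole day from −3 to +3, equally likely and independent (an assumption), giving 7 × 7 = 49 pairs.

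- The gap is below 137 when the second offset minus the first is −4, −5 or −6: 3 + 2 + 1 = 6 pairs, and 6/49 = 12.2%.
- With one day added to the count, only −5 and −6 fail: 2 + 1 = 3 pairs, and 3/49 = 6.1%.

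**4. Which pairs are affected.**

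| Pair | Nominal gap (days) | In-window range (days) |
|---|---|---|
| Week 5 to 13 | 56 | 50–62 |
| Week 13 to 25 | 84 | 78–90 |
| Week 5 to 25 | 140 | 134–146 |
| Week 13 to 37 | 168 | 162–174 |
| Week 25 to 49 | 168 | 162–174 |
| Week 5 to 37 | 224 | 218–230 |

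Only Week 5 to Week 25 straddles 137. Shorter pairs never qualify and longer ones always do. The shortfall therefore affects only subjects who respond at Week 5 and Week 25 and have no later qualifying response.

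**5. The SD allowance.** Week 13 is the only scheduled assessment between Weeks 5 and 25. Take the Appendix H skin rules with a baseline of 60% BSA:

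- 25% is PR, since 25/60 = 0.42, which is at most 0.5.
- 60% is SD, and so is 80%, since 80 − 60 = 20 is less than 25.
- 85% would be PD, since 85 − 60 = 25.

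The sequence 25%, 60%, 25% at Weeks 5, 13 and 25 counts as sustained if the visits are at least 137 days apart. PR, SD, SD, PR over Weeks 5 to 37 also counts.

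**6. Effect on the test.** The design assumes a 50% response rate in 40 subjects (SAP 1.4), so 0.5 × 40 = 20 responders. The exact 95% lower bound is 27.2% for 10/20 (objective met) and 23.1% for 9/20 (not met). One reclassified subject can change the conclusion.

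**The case against.** **The tolerance is minor and depends on conventions that the SAP leaves open.** This is right. The SAP does not say whether the interval ends at the last response, at progression or at censoring, nor whether a day is added; it does add one for treatment duration and time on study (SAP 3.1.4 and 3.1.5). If the interval ended as DOR does in SAP 5.2.2, the problem would largely disappear. A later response also rescues the subject, and the error makes the endpoint harder to meet. It can also be said that 134 days lies further from the protocol's five months. But the SAP has already chosen to allow for the visit window, and its figure does so for only one of the two visits.

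**The SD allowance is deliberate.** It is prespecified. Protocol 5.3.3 describes a disease that waxes and wanes, and DOR likewise ends at progression or death rather than at SD. Only SD bracketed by responses is allowed, so a response that is never regained gains nothing. SD can also be a trivial threshold crossing: from a baseline of 30% BSA, 5% is PR (30 − 5 = 25) and 6% is SD (30 − 6 = 24). This is a fair case for keeping the tolerant definition as the tested one. It does not reconcile the rule with the word 'continuously', nor explain its absence from the protocol.

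**A stronger reading.** A reader might infer that the SD allowance by itself carries the endpoint across the 25% criterion. For instance, suppose each later visit is in response with probability 0.4. A strict rule then gives 0.4 × 0.4 = 16% and the tolerant rule 40%. The documents do not support this. The 25% applies to the lower confidence bound, so an observed 40% fails too: 8/20 has a lower bound of 19.1% and 16/40 has 24.9%. The calculation also assumes that a subject's visits are independent, which is implausible for repeated scores against one baseline, and it ignores intervals that qualify after Week 25.

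**Conclusion.** The point holds in two limited parts.

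First, the tolerance is 3 days too small for its stated purpose. The 134-day minimum gap follows from the schedule. The 12% (or 6%) is a share of Week 5 to Week 25 pairs under uniform, independent visit timing, not a share of all responders. It assumes that the interval runs from first to last response assessment.

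Second, the SAP's wording is internally inconsistent, and its SD allowance is not in the protocol definition. This is a matter of definition rather than an arithmetical error. The documents give no data on how responses change from visit to visit, so the rise in the rate due to the SD rule cannot be estimated from them. What can be said is that, near the boundary with about 20 responders, a single subject is enough to change the result.

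**What to change.** - Set the bound at 134 days, or define the criterion by visit: response at Week 5 through Week 25, or at a later pair of visits at least as far apart.
- State the start and end of the interval and whether a day is added in counting.
- Reconcile 'continuously' with the SD allowance, so that the text says which is meant.
- Prespecify a sensitivity analysis that requires CR or PR at every scheduled assessment in the interval, and report it beside the SD-tolerant rate.

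All of this is SAP wording and programming on assessments already scheduled; no new data are needed. The cost is that the strict rate will be somewhat lower than the tolerant one.

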5.2.2 Duration of Response

Duration of Response (DOR) is defined as the interval between the date of initial documentation of a response, and the date of first documented evidence of progressive disease, death, or date of censoring if applicable, for responders only. The distribution (median and Kaplan-Meier curve) will be provided using Kaplan-Meier estimates to evaluate DOR. DOR will be right censored based on [Table 1](#) for all responders:

Table 1: Date of Event or Censoring for Duration of Response

Situation	Date of DOR event or Censoring	Outcome
Death or disease progression occurred on or before the start date of subsequent cGVHD treatment documented at scheduled disease assessments or between two scheduled disease assessments.	Earliest date of adequate disease assessment documenting disease progression or date of death, whichever occurs first.	Progressed
New subsequent cGVHD treatment before disease progression	Date of last adequate disease assessment prior to or on start date of the new subsequent cGVHD treatment	Censored
Not known to have progressed or died at the data analysis cutoff date (this includes subjects who were known to have progressed or died after the data analysis cutoff date)	Date of last adequate disease assessment showing no evidence of disease progression.	Censored

For subjects who met more than one censoring condition, DOR will be censored according to the earliest censoring condition/date. For subjects who have incomplete date for initiation of subsequent cGVHD treatment, the partial date will be imputed as the earliest possible date that incorporates the available information from the partial date and does not contradict last dose date of study drug.

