A recently published single institution study developed a new approach for evaluating clinical trial endpoints for testing therapies for second-line treatment of cGVHD (Inamoto 2013). The primary study endpoint was failure free survival (FFS) defined as the absence of a third line therapy, NRM, and recurrent malignancy. This was a retrospective study of 312 patients at the Fred Hutchinson Cancer Research Center who had received systemic steroids for the treatment of cGVHD at a dose of at least 0.5 mg/kg/day before second line treatment, were on systemic immunosuppressive therapy when the second line therapy was initiated, and had received second line therapy due to cGVHD progression after at least one week of initial therapy or due to lack of improvement after at least two weeks of initial therapy. FFS was reported at 56% at 6 months and at 45% at 12 months from the start of second line therapy (Inamoto 2013). With 48 months of follow-up, only 15% of patients were able to successfully withdraw from all immunosuppressive therapy. The major cause of FFS was treatment change (ie, need for third line therapy) and the study results have set a benchmark for second line cGVHD therapy (Inamoto 2013).

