7.2. Efficacy Evaluations

7.2.1. NIH Response Criteria (see [Appendix F](#) and [Appendix G](#))

All subjects in the study will have their response assessed using the NIH cGVHD Response assessment ([Pavletic 2006](#); [Measurement of Therapeutic Response, ASBMT Web site](#)) at baseline, at week 5, and after every 12 weeks of therapy. Response will be determined by the following criteria:

1. Complete Response – Complete resolution of all reversible manifestations of cGVHD. Irreversible manifestations will be defined by NIH consensus criteria ([Pavletic 2006](#)) (eg, ocular xerosis, esophageal stricture, and bronchiolitis obliterans).
2. Partial Response – At least a 25% absolute or 50% relative change (whichever is greater) when comparing start and end measurements in one cGVHD domain without worsening in the other domains ([Appendix H](#)).
3. Stable Disease – No worsening in baseline cGVHD manifestations.
4. Progressive Disease – Worsening in any one cGVHD domain by at least an absolute change of 25% from baseline unless baseline values are within 25% of the scale used to score cGVHD. In addition, a new cGVHD manifestation also counts as progression ([Appendix H](#)).

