10.2.2.2. Duration of Response (DOR)

Duration of response is defined as the interval between the date of initial documentation of a response, and the date of first documented evidence of progressive disease, death, or date of censoring if applicable, for responders only. Percentage of subjects with sustained response and its 95% confidence interval will be calculated using normal approximation to the binomial distribution. Subjects who stop the study drug and start new GVHD treatment before documentation of disease progression will be censored on the date of the last adequate disease assessment that is on or before the start date of new GVHD therapy. Responders are subjects who achieve a NIH-defined complete response or partial response during the study. Non-responders will be excluded from the analysis for DOR.

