****Score changes from 0 to 1 are not considered progression.**

*s, starting score or value; e, ending score or value; ULN, upper limit of normal

† If the starting lung function score is ≥ 10 , progression is defined as $\geq 5\%$ decrease of FEV1 in two tests measured at least 2 weeks apart. This time interval was selected because these syndromes can progress rapidly.

http://asbmt.affiniscape.com/associations/11741/files/ResponseCriteriaAPPENDIXC_DCCalculations.pdf

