Appendix I. Guidelines for Chronic GVHD Activity Assessment – Clinician (FORM A)

Any measure that is normal and does not have cGVHD involvement at Day 1 = NE (not evaluable), remains NE unless criteria for PD is met.

Any measure that changes but is not felt to be related to cGVHD should be marked as NE. Organs with more than one component will have each component evaluated, and then an organ score will be assigned.

Overall cGVHD assessment: SD: no PR, no PD, no CR

PR: if no PD and ≥ 1 PR

PD: if ≥ 1 PD

CR: all CR

Measures	Individual Response*	Overall organ response
Skin (percent of body surface) Body surface area of erythematous rash		NE: no cGVHD SD: no PR, no PD, no CR
Skin Body surface area of moveable sclerosis		PR: if no PD and ≥ 1 PR
Skin Body surface area of non-moveable sclerosis		PD: if ≥ 1 PD CR: all CR
Eyes – Right eye Schirmer Tear Test (mm wetting)		NE: no cGVHD
Eyes – Left Eye Schirmer Tear Test (mm wetting)		SD: no PR, no PD, no CR PR: if no PD and ≥ 1 PR PD: if ≥ 1 PD CR: all CR
Mouth Mucosal change (Scores range from 0-15)		NE: no cGVHD SD: no PR, no PD, no CR PR PD CR
Blood Counts Platelet count and absolute eosinophil count		NE: no cGVHD SD: no PR, no PD, no CR PR: if no PD and ≥ 1 PR PD: if ≥ 1 PD CR: all CR
Liver Function Tests ALT, total serum bilirubin and alkaline phosphatase		NE: no cGVHD SD: no PR, no PD, no CR PR: if no PD and ≥ 1 PR PD: if ≥ 1 PD CR: all CR
GI – Upper		NE: no cGVHD SD: no PR, no PD, no CR
GI – Esophageal		PR: if no PD and ≥ 1 PR
GI – Lower		PD: if ≥ 1 PD CR: all CR
Lung response Pulmonary Function Tests with Diffusing Capacity, FEV1 and DLCO		NE: no cGVHD SD: no PD PD No possible PR or CR
Overall cGVHD Response		SD: no PR, no PD, no CR PR: if no PD and ≥ 1 PR PD: if ≥ 1 PD CR: all CR

*See [Appendix H](#) for individual response

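### Duration of response ends only at progression from baseline or at death, so a lost response keeps running and a switch to new cGVHD therapy is censored

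*SAP*

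**What the plan says.** SAP 5.2.2 and protocol 10.2.2.2 agree on the definition. DOR runs from first documented response to the "date of first documented evidence of progressive disease, death, or date of censoring if applicable, for responders only".

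Progression is defined in protocol 7.2.1 as "Worsening in any one cGVHD domain by at least an absolute change of 25% from baseline", with the exception "unless baseline values are within 25% of the scale used to score cGVHD"; a new manifestation also counts. Appendix H turns this into formulas in two quantities only: "s, starting score or value; e, ending score or value; ULN, upper limit of normal". None refers to the best value reached. Appendix I classes an overall assessment meeting none of the other categories as stable: "SD: no PR, no PD, no CR".

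SAP Table 1 has three rows. Progression or death on or before the start of subsequent cGVHD treatment is an event. New cGVHD treatment before progression is censored at the last adequate assessment on or before its start. A subject not known to have progressed or died is censored at the last adequate assessment without progression. Protocol 10.2.2.2 likewise says that a subject who stops study drug and starts new GVHD treatment before progression "will be censored on the date of the last adequate disease assessment that is on or before the start date of new GVHD therapy".

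Two neighbouring endpoints treat the same outcomes differently. Sustained response (SAP 5.2.1) must be continuous, with SD tolerated only between response assessments. Failure-free survival (SAP 5.3) counts new subsequent cGVHD treatment as an event.

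**The concern.** A reader will take the DOR curve as showing how long responses last. As defined, it shows time from response until the subject is measurably worse than at study entry, or dead. The two differ for any responder who loses the improvement without passing the starting value by the progression margin.

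The second issue is censoring at new therapy. Kaplan-Meier assumes that censored subjects carry the same future risk as those who remain. A responder given another cGVHD treatment has plausibly lost adequate control, so the censoring is plausibly informative. In describing its second-line benchmark cohort, the protocol (1.5) says "The major cause of FFS was treatment change", evidently meaning the major cause of failure.

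Both features act in the same direction, towards a longer apparent duration. At stake is the interpretation of a secondary endpoint. The primary response rate and the formally tested sustained-response rate are unaffected.

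**Working it through.** The plan gives no median, rate, event count or target for DOR, so there is no planned figure to reproduce. The check applies the plan's own rules.

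**1. Inputs (Appendix H; s = start, e = end).**
- Skin PR: for s > 50, e/s ≤ 0.5 and e > 0. Skin progression: e − s ≥ 25. Maximum 100.
- Mouth PR: for s ≥ 8, e/s ≤ 0.5 and e > 0; for s from 4 to 7, s − e ≥ 4 and e > 0. Mouth progression: e − s ≥ 3. Maximum 15.

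**2. Response lost without progression.**
- Skin 60 → 30: 30/60 = 0.50, PR. Back at 60: 60 − 60 = 0. At 84: 84 − 60 = 24 < 25. Neither is progression; 85 is the first value that qualifies.
- Mouth 6 → 2: 6 − 2 = 4, PR. Back at 6: 0. At 8: 8 − 6 = 2 < 3. Neither is progression; 9 is the first value that qualifies.

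In these ranges PR no longer holds, and Appendix I gives SD if no other measure responds or progresses. DOR continues.

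**3. Scale ceiling, one measure at a time.**
- Skin: the largest possible rise is 100 − s, which reaches 25 only if s ≤ 75. Example: 80 → 40 is PR (40/80 = 0.50), then 100 gives 100 − 80 = 20 < 25.
- Mouth: the largest possible rise is 15 − s, which reaches 3 only if s ≤ 12. Example: 13 → 6 is PR (6/13 = 0.46), then 15 gives 15 − 13 = 2 < 3.

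**4. Side by side with SAP 5.2.1.** Take a subject with PR at Week 5 (target Day 29, SAP 8.1) and SD at Weeks 13, 25, 37 and 49 (target Day 337). No later response follows, so the SD is not between response assessments and the subject is not a sustained responder. Under Table 1 the same subject contributes 337 − 29 = 308 event-free days to DOR.

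**5. Direction and possible size, on assumed data.** Take 20 responders (50% of 40, the planning assumption) assessed every 3 months. Six have progression or death at months 3, 6, 6, 9, 12 and 12. Without progression, k subjects start new therapy (first k of months 4, 5, 7, 8) and k others fall back to SD (first k of months 3, 6, 6, 9). Everyone else is followed to month 18.

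Worked case, k = 2:
- SAP rule: the two switchers are censored back to month 3, leaving 17 at risk at month 6, 15 at month 9 and 14 at month 12. The estimate is 19/20 × 15/17 × 14/15 × 12/14 = 0.671.
- New therapy as an event: (20 − 6 − 2)/20 = 0.600.
- New therapy and loss of response as events: (20 − 6 − 2 − 2)/20 = 0.500.

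| k | SAP rule | New therapy as event | Both as events | SAP rule minus both |
|---|---|---|---|---|
| 1 | 0.686 | 0.650 | 0.600 | 0.086 |
| 2 | 0.671 | 0.600 | 0.500 | 0.171 |
| 3 | 0.659 | 0.550 | 0.400 | 0.259 |
| 4 | 0.645 | 0.500 | 0.300 | 0.345 |

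These are month-12 estimates. The counts and times are invented to show the mechanism; none comes from the documents.

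**The case against.** The strongest case for the plan is as follows. The definition is stated openly and identically in both documents, and the baseline reference belongs to the adopted consensus criteria. Protocol 5.3.3 explains that cGVHD waxes and wanes, so ending a response at every dip would be too harsh. DOR is descriptive, with no test (SAP 5.2). Sustained response already requires continuity, and failure-free survival already counts new treatment. Protocol 8.2.1 calls for a visit with NIH assessment whenever progression is suspected or treatment stops, and 8.2.2 for another at 30 days from the last dose or before a new cGVHD treatment. Many switches may therefore have progression recorded first, which makes them events.

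Much of this stands. It limits the weight of the point, and the argument about transient dips shapes the remedy. It does not remove the gap. Failure-free survival is exploratory, is not restricted to responders, and does not count loss of response without new therapy. Sustained response is a yes/no classification at about five months. The only general efficacy sensitivity analysis (SAP section 5) changes the analysis set, not the event definition.

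Three stronger readings are tempting, and the documents do not support them.
- *Switchers go on lengthening DOR.* They do not. Table 1 censors them at the last adequate assessment on or before the new therapy, and if progression was documented by then they are events.
- *Progression is impossible near the scale ceiling.* This holds only for that single measure. Progression in another domain, in another skin measure or through a new manifestation still counts. The documents do not say how many subjects start so high.
- *The bias can be sized from the 45% failure-free rate at 12 months in protocol 1.5.* That figure covers all patients in a retrospective second-line cohort, from start of therapy, with different events. No document gives the share of treatment changes among responders that occur without documented progression.

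**Conclusion.** The point holds. DOR under SAP 5.2.2 is time from first response to worse-than-baseline disease or death. It keeps accruing after a response is lost, and it censors new therapy started without documented progression. The first part follows directly from the definitions. The second depends on the judgement that starting new cGVHD therapy is related to failing control, which is plausible but not shown in the documents. Labelled as duration of response, the Kaplan-Meier estimate can overstate durability.

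The size is unknown. It depends on how many responders return to SD without recovering, and how many switch without recorded progression. Neither number is given, so the range in the table illustrates direction only. The weight is moderate, because DOR carries no alpha and no success criterion.

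**What to change.** Keep the present analysis in SAP 5.2.2, relabelled *time from response to progression or death*. Add a co-reported DOR with these events, whichever comes first:
- loss of CR/PR versus baseline, dated at the first SD assessment not followed by a later CR/PR. An SD assessment followed by a later CR/PR is not an event, matching SAP 5.2.1;
- progressive disease;
- death;
- start of new systemic cGVHD therapy.

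The intermittent-SD rule is essential. Without it, a subject with PR, SD, PR could be a sustained responder under 5.2.1 and yet end DOR at the SD visit. Report the number of responders by event type under both definitions, so the reader can see what separates the curves.

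The cost is one more descriptive Kaplan-Meier analysis and a probably shorter reported duration. No new data are needed: NIH assessments continue every 12 weeks until progression, including after stopping for other reasons (protocol 8.3.1), and subsequent cGVHD therapies are recorded for subjects who stop without progression (protocol 7.1.5).
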